**Abbreviations**

CM=Cyclical Mastalgia, VAS-BP=Breast Pain VAS, Nominal Days of Breast Pain=NDBP, WHOQOL-BREF= World Health Organization Quality Of Life Scale-Short Form, QOL= Quality Of Life, MA= Manual Acupuncture, SA= Sham Acupuncture, CRF= Case Report Form

## Statistical Analysis Plan

Statistical methods for primary and secondary outcomes

We will use SPSS 22.0 software (IBM SPSS Statistics; IBM Corp, Somers, NY) to perform all statistical analyses following the intention-to-treat principle. The CI will be established at 95%, and the significance level at 0.05. For continuous data, the data will be presented as mean  $\pm$  standard deviation when normally distributed or presented as median (IQR) when not normally distributed. Statistical comparisons will be performed by the independent-sample t tests or Wilcoxon rank-sum test for continuous data and by X-test or Fisher exact test for categorical data, as appropriate. A p-value  $<0.05$  will be considered statistically significant.

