## **Type of Units Assigned**

### **Period(s)**

The duration of the trial is 38 weeks for each patient, including a 2-week baseline assessment (week 0-2), 12-week treatment period (week 1-12), and 24-week follow-up (week 13-36).

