### **2. Baseline Characteristics**

Personal information including age, marriage, menstrual, and medical history and a series of questionnaire including VAS-BP in the first two weeks of menstruation, the number of nominal days of breast pain (NDBP) two weeks before menstruation, World Health Organization Quality Of Life Scale-Short Form (WHOQOL-BREF) scores, breast glandular section thickness and breast duct width three days before menstruation are cautiously recorded.

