### **3. Outcome Measures**

#### **Primary outcome**

The primary outcome in this trial is the change in the average of VAS-BP scores in the first 2 weeks of menstruation, recorded in the patient daily diary.

The VAS-BP will be measured using a 10cm linear VAS with 0 representing no pain and 10 the worst imaginable pain from baseline at weeks 4, 8, and 12.

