#### **Secondary outcomes**

1. The changes in the number of nominal days of breast pain (NDBP) during 2 weeks before menstruation from baseline at weeks 4, 8, 12.

2. The changes of WHOQOL-BREF scores from baseline at weeks 12. The

WHOQOL-BREF china version will be used to evaluate the QOL of the participants. The WHOQOL-BREF Questionnaire consists of 26 items, in which the first and second questions of the questionnaire are about the QOL and health status in general. The next 24 questions assess the QOL in four dimensions: physical health (7 items); psychological (6 items); environment (8 items); and social relationships (3 items). Each item is answered on a five-point scale. A higher score denotes a better quality of life [3-4].

3. The changes in breast glandular section thickness, and breast duct width three days before menstruation from baseline at weeks 12.

Mammary ultrasonography will be used to observe breast glandular section thickness, and breast duct width. All ultrasound image acquisition work is completed by the same ultrasound physician with at least 5 years of professional practice.

4. Patients' global improvement assessment: It will be assessed by a 7-point self-reporting scale ranging from 1 to 7: significantly reduced, moderately reduced, slightly reduced, no change, slightly aggravated, moderately aggravated, and significantly aggravated. The proportion of patients reporting "significantly reduced" or "moderately reduced" is recorded as the response rate of overall efficacy.

5. Patients' acceptability toward acupuncture at the end of the 1st treatment at week 1 and the last treatment at week 12. The acceptability of acupuncture will be assessed among participants in the MA group using a 3-point index: unacceptable (0 points), acceptable (1 point), and easy to accept (2 points). Those who regard acupuncture as unacceptable will report the reasons. The average score will be calculated after the 2

assessments.

6. Blindness assessment: within 3 min after the last treatment session at week 12, all participants will be asked to answer the question do you think you have received acupuncture treatment and choose the answer between the options of Yes or No.

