### **Statistical analysis**

Sample size estimation was based on changes in the breast pain VAS(VAS-BP) score. According to the pre-trial, the VAS-BP score significantly decreased by  $2.98 \pm 0.95$  in MA group compared to  $2.35 \pm 0.97$  in the SM group after treatment from baseline. In the current trial, we assume a significance level  $\alpha = 0.05$  and power  $(1-\beta) = 0.90$ , and providing for a two-sided outcome, at least 42 participants will be required for each group, as calculated by PASS version 11.0 (NCSS, LLC, Kaysville, UT, USA), assuming a two-tailed test with a 20% drop-out rate, a total of 108 patients (54 in each group) will be recruited.

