#### 5. Results Point of Contact

[name], Chief physician, Department of Acupuncture and Moxibustion, Beijing Pinggu District Hospital of Traditional Chinese Medicine, 101200, Beijing, China.[name], [[contact]](mailto:[contact])

Figure 1. Flow chart of participants through the proposed trial.

The schedule of the whole procedure is shown in Table1

Table1 Study period.

	STUDY PERIOD						
	Enrolment	Allocation	Treatment			Follow up	
Timepoint(W,week)	-2	0	4	8	12	24	36
ENROLMENT							
Eligibility screen	X						
Informed consent	X						
Allocation		X					
Interventions							
Manual acupuncture			◆—————◆				
Sham acupuncture			◆—————◆				
Assessment							
VAS-BP	X	X	X	X	X	X	X
NDBP	X	X	X	X	X	X	X
WHOQOL-BREF		X			X		
Breast glandular thickness		X			X		
Breast duct width		X			X		
Patients' global improvement assessment					X		
Patients'acceptability			X		X		
Blindness assessment					X		
Safety assessment			X	X	X	X	X

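### The primary comparison of change in VAS-BP ignores baseline VAS-BP as a covariate; adding it would usually sharpen the estimate at no cost in data, by an amount the documents do not allow us to fix

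*Combined protocol and SAP*

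**What the plan says.** The primary outcome is a change score: "The primary outcome in this trial is the change in the average of VAS-BP scores in the first 2 weeks of menstruation". The same section places the measurement at three times, "10 the worst imaginable pain from baseline at weeks 4, 8, and 12", and names none of them as primary.

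The protocol's section on statistical methods for primary and secondary outcomes and the Statistical Analysis Plan carry the same text: "Statistical comparisons will be performed by the independent-sample t tests or Wilcoxon rank-sum test for continuous data", with the choice between the two left to what is appropriate. Neither mentions a covariate, regression, ANCOVA or mixed model. The protocol marks additional analyses as not applicable.

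The baseline values exist. Section 2, Baseline Characteristics, lists "a series of questionnaire including VAS-BP in the first two weeks of menstruation", together with NDBP, WHOQOL-BREF and the two ultrasound measures. The VAS-BP and NDBP rows of Table 1 are marked at both week -2 and week 0. The Period(s) section describes "a 2-week baseline assessment (week 0-2), 12-week treatment period (week 1-12", so the stated baseline and treatment windows overlap.

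Secondary outcomes 1 to 3 are also changes from baseline, for example "The changes of WHOQOL-BREF scores from baseline at weeks 12". The Statistical analysis section says "Sample size estimation was based on changes in the breast pain VAS(VAS-BP) score" and gives the mean and SD of the change in each arm. It gives no baseline SD, follow-up SD or correlation.

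**The concern.** Subtracting baseline is not the same as adjusting for it. A change score fixes the coefficient on baseline at 1, whereas ANCOVA estimates it. In large samples the ANCOVA estimate has variance no larger than that of the change-score comparison; the two are equal only when baseline is uncorrelated with change. Pain scores commonly regress to the mean, so patients with higher baseline pain tend to show larger falls, and part of the spread in the change scores is then predictable from a value already in the database.

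Two things are at stake. The confidence interval for the primary effect may be wider than the collected data require. The point estimate also moves with any chance difference in baseline pain between arms. In addition, because the choice between the t test and the Wilcoxon test is left open, no single primary test is fixed before the data are seen.

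**Working it through.** **Inputs** (protocol, Statistical analysis section): change 2.98 ± 0.95 with manual acupuncture and 2.35 ± 0.97 with sham; two-sided alpha 0.05; power 0.90; 42 per arm needed; 54 per arm recruited after 20% dropout.

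**Step 1: the plan's own figure.** Difference = 2.98 − 2.35 = 0.63. Pooled SD = √((0.95² + 0.97²)/2) = 0.960. Standardised effect = 0.63/0.960 = 0.656. Two-sided 90% power needs 49 per arm by the normal formula and 50 by the t distribution, so the stated 42 is not reproduced. That is a separate error. It is noted here only because it sets the reference power.

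**Step 2: power of the planned t test** (noncentral t).

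| Analysed per arm | Power |
|---|---|
| 42 | 84.4% |
| 43 (54 × 0.8 = 43.2) | 85.3% |
| 54 | 92.2% |

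At 43 per arm the standard error is 0.960 × √(2/43) = 0.207, and the 95% CI half-width is 1.989 × 0.207 = 0.41 points.

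**Step 3: variance with baseline adjustment.** Let r be the correlation between baseline and follow-up, k the ratio of follow-up SD to baseline SD, and s the baseline SD.

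- Variance of change: s²(1 + k² − 2rk).
- ANCOVA residual variance: s²k²(1 − r²).
- Ratio: k²(1 − r²)/(1 + k² − 2rk). For k = 1 this reduces to (1 + r)/2.

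The SD of change stays at 0.960, so the standardised effect becomes 0.656/√ratio. **The documents give neither r nor k; both are assumed over a range.** Results at 43 per arm:

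| r | k = 1: ratio | power | half-width | k = 1.2: ratio | power | k = 0.8: ratio | power |
|---|---|---|---|---|---|---|---|
| 0.3 | 0.65 | 96.2% | 0.33 | 0.762 | 93.1% | 0.502 | 98.9% |
| 0.5 | 0.75 | 93.5% | 0.36 | 0.871 | 89.7% | 0.571 | 97.8% |
| 0.7 | 0.85 | 90.4% | 0.38 | 0.966 | 86.4% | 0.628 | 96.7% |
| 0.8 | 0.90 | 88.7% | 0.39 | 0.997 | 85.4% | 0.640 | 96.4% |
| 0.9 | 0.95 | 87.0% | 0.40 | 0.977 | 86.1% | 0.608 | 97.1% |

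For k = 1.2 and r = 0.8 the half-width is 0.41 × √0.997, still 0.41: no visible gain. Losing one degree of freedom to the covariate changes power by at most 0.1 percentage point.

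**Step 4: where ANCOVA reaches 90% power.** With k = 1, r must be at most 0.72 at 43 per arm, or 0.68 at 42. With k = 1.2 the limits are about 0.48 and 0.44. If all 54 per arm are analysed, ANCOVA with k = 1 has 98.7% to 93.4% power over r = 0.3 to 0.9, against 92.2% for the planned test.

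**Step 5: exposure to chance imbalance** (k = 1, 43 per arm). Baseline SD s = 0.960/√(2(1 − r)). A baseline difference of one standard error, s√(2/43), moves the change-score estimate by (1 − r) × s√(2/43) = 0.12, 0.10, 0.08, 0.07 and 0.05 points for r = 0.3, 0.5, 0.7, 0.8 and 0.9, against an assumed effect of 0.63. The standard error of the change-score test already includes this variation, so it is not a bias.

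**The case against.** The strongest reply is that nothing here is invalid. The outcome is defined as a change, the trial was sized on changes, and a t test on changes is consistent with both. Type I error is not affected, and baseline is already used through subtraction. That stands, and it is why the point concerns efficiency and not correctness.

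Second, the size of the benefit cannot be derived from the documents. That also stands. With a follow-up SD 1.2 times baseline and r = 0.8, power moves only from 85.3% to 85.4%. A statement that the interval will be materially narrower would go too far; the large-sample result supports only that it will be no wider.

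Third, the 85.3% reference depends on the sample size error and on 43 patients per arm being analysed. The protocol's section on missing data mentions both complete-case and intention-to-treat analysis, and with all 54 per arm the planned test already exceeds 90%. This is fair: ANCOVA should not be presented as the repair for the sample size.

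Fourth, the unnamed primary time point and the unclear baseline would need settling under any test. That is true, and they do not make this point more serious. They belong here only because an adjusted model cannot be written down without them. As for t versus Wilcoxon, a choice driven by normality is the natural reading, but no rule for it is written.

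**Conclusion.** The concern holds. The protocol and SAP plan only an unadjusted comparison of change in VAS-BP, baseline VAS-BP is collected, and no baseline-adjusted analysis appears anywhere. The planned test is valid but usually less precise than the data allow.

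At equal SDs, for r from 0.3 to 0.9, ANCOVA would cut the variance by 35% to 5%. At 43 per arm it would raise power by 10.9 to 1.7 percentage points (96.2 − 85.3 and 87.0 − 85.3). The gain is larger if the follow-up SD is smaller than the baseline SD, and can be close to nil if it is larger. These figures rest on the protocol's change-score inputs and on assumed values of r and k. Confidence is high that the adjustment is missing and worth adding; the size of the gain is unknown. The change should be made, but the trial's validity does not depend on it.

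**What to change.** Before the data are seen, prespecify in the SAP:

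- **One primary test.** Either an ANCOVA of week-12 VAS-BP (or its change) on treatment with baseline VAS-BP as covariate, or a repeated-measures model over weeks 4, 8 and 12 with the same covariate and a named primary contrast.
- **The primary time point**, since the primary outcome section lists three.
- **The definition of baseline**: the week -2 value, the week 0 value or their mean. Reconcile this with the Period(s) section, where the baseline and treatment weeks overlap.
- **Reporting**: the adjusted difference with its 95% CI, with the Wilcoxon test kept as a sensitivity analysis.
- **Secondary outcomes**: the same adjustment for WHOQOL-BREF, the ultrasound measures and NDBP. Check model fit for NDBP, which is a count of days bounded by its two-week window.

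The cost is one degree of freedom, SAP wording and two decisions (time point and baseline). No new data, visits or patients are needed. The sample size calculation has to be corrected separately.
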